| | 
• Endovenous glue induced thrombosis (EGIT) or endovenous heat induced thrombosis (EHIT)• Symptomatic deep vein thrombosis (DVT) events 
7. Additional events evaluated through 60 months (through 12 months for VenaSeal vs. Surgical Stripping Study)
 
• Symptomatic Pulmonary embolism (PE)• Serious adverse events (SAEs) 
Healthcare utilization secondary endpoints
 
8. Number and type of adjunctive treatments conducted through 12 months post-index procedure.9. Healthcare utilization related to the target limb VRD, as determined by the number of healthcare visits conducted, and other health-related resources utilized (e.g., home healthcare services) between study visits through 60 months (through 12 months for VenaSeal vs. Surgical Stripping Study).10. Procedures, tests and treatment of AEs related to the treatment modality or index procedure through 60 months (through 12 months for VenaSeal vs. Surgical Stripping Study).11. VLU Study: Healthcare utilization and routine wound care treatments between study visits through 60 months. 
Patient Experience secondary endpoints
 
12. Time to return to normal activities as reported by the patients.13. Intra-procedural and post-procedural pain at the index procedure, and pain at 7 and 30 days as reported by the patient using the numeric rating scale (NRS) with a scale of 0-10.14. Change in venous disease symptoms at 7 and 30 days, and at 6, 12, 24, 36, 48, and 60 months compared to baseline (7 and 30 days, 6 and 12 months only for VenaSeal vs. Surgical Stripping Study), as measured by the revised Venous Clinical Severity Score (rVCSS) and subject self-reporting.15. Change in AVVQ score at 30 days, and 6, 12, 24, 36, 48, and 60 months (30 days, 6 and 12 months only for VenaSeal vs. Surgical Stripping Study) compared to baseline.16. Change in EuroQoL Group 5-Dimension Self-Report Questionnaire (EQ-5D-5L) at 30 days, and 6, 12, 24, 36, 48 and 60 months (30 days, 6 and 12 months only for VenaSeal vs. Surgical Stripping Study) compared to baseline. |
|--|--|

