10. VenaSeal-treated subjects: points of aneurysm, tributaries, or perforators per target vein when multiple VenaSeal™ aliquots are utilized.
11. Post-procedure DUS: assessment of patency, stump length, reflux along treatment area, evidence of thrombus.
12. Post-procedure measurement of actual treatment length using a tape measure to measure the difference between the clinically relevant lowest point of reflux to the access point.
13. Physician satisfaction with the procedure.
14. AE assessment from the moment the index procedure was initiated.
15. VenaSeal™ system treated subjects: Device deficiencies related to the VenaSeal™ system.
16. Treatment issues experienced by the treating physician.
17. Subject's use of compression stockings upon discharge.

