11.5. Risk-Benefit Rationale

The probable benefits of the VenaSeal™ closure system are based on outcomes reported in the VeClose Pivotal IDE study as well as the Feasibility and eSCOPE studies described in section 4.1, Background. These data were used to support regulatory approval of the VenaSeal™ system. The use of the VenaSeal™ system to treat VRD in the GSV, a superficial truncal vein, resulted in high closure rates, and these results are consistent with the reported closure success rates with ETA treatments (i.e., RFA, EVLA). In addition, the VenaSeal™ system addresses some challenges associated with current ETA technologies such as less bruising (echymosis) and rapid return to normal activities without the need for compression stockings following treatment.^{33,34} The risks are similar to RFA, which is currently a commonly-used and comparative treatment modality that will be allowed as part of the ETA arm in this study.

Regarding study participation, subjects are not put at any additional risk for participating in the study, as compared to being treated with the VenaSeal™ system, through ETA, or a surgical stripping treatment as part of their routine care. Subjects for whom it is unethical to be randomized to one of the treatment arms, should not be included in this study. Subjects who are included in this study will receive an increased level of care from their physicians as a result of participation, specifically additional follow-up visits and AE assessments.

Given the available information above, the data support that for use in the treatment of lower extremity symptomatic varicose veins, the probable benefits of treatment with the VenaSeal™ system, treatment with ETA, or treatment through a surgical stripping procedure outweigh the probable risks.

12. Adverse Events and Device Deficiencies

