V  1  2  3  4
W  1  2  3  4

Right

Y  1  2  3  4
Z  1  2  3  4
AA  1  2  3  4
BB  1  2  3  4
CC  1  2  3  4
DD  1  2  3  4
EE  1  2  3  4
FF  1  2  3  4

Medtronic Business Restricted

CONFIDENTIAL

056-F275, v B Clinical Investigation Plan Template

VENASEAL SPECTRUM Clinical Investigation Plan

MDT18034

Version 5.0

Page 128 of 164

Medtronic

H 1 2 3 4

P 1 2 3 4

X 1 2 3 4

FF 1 2 3 4

2. In the last two weeks for how many days did your veins cause you pain or ache?

	Right Leg	Left Leg
None at all		
Between 1 and 5 days		
Between 6 and 10 days		
For more than 10 days		

3. During the last two weeks, how many days did you take painkilling tablets for your varicose veins?

	Right Leg	Left Leg
None at all		
Between 1 and 5 days		
Between 6 and 10 days		
For more than 10 days		

4. In the last two weeks, how much ankle swelling have you had?

 None at all
 Between 1 and 5 days
 Between 6 and 10 days
 For more than 10 days

5. In the last two weeks, have you worn support stockings or tights?

	Right Leg	Left Leg
No		

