	None: 0	Mild: 1	Moderate: 2	Severe: 3
Pain or other discomfort (i.e. aching, heaviness, fatigue, soreness, burning) Presumes venous origin		Occasional pain or other discomfort (i.e. not restricting regular daily activities)	Daily pain or other discomfort (i.e. interfering with but not preventing regular daily activities)	Daily pain or discomfort (i.e., limits most regular daily activities)
Varicose Veins “Varicose” veins must be ≥ 3 mm in diameter to qualify in the standing position		Few: scattered (i.e., isolated branch varicosities or clusters) Also includes corona phlebectatica (ankle flare)	Confined to calf or thigh	Involves calf and thigh
Venous Edema Presumes venous origin		Limited to foot and ankle area	Extends above ankle but below knee	Extends to knee and above
Skin Pigmentation Presumes venous origin Does not include focal pigmentation over varicose veins or pigmentation due to other chronic diseases (i.e., vasculitis purpura)	None or focal	Limited to perimalleolar area	Diffuse over lower third of calf	Wider distribution above lower third of calf
Inflammation More than just recent pigmentation (i.e., erythema, cellulitis, venous eczema, dermatitis)		Limited to perimalleolar area	Diffuse over lower third of calf	Wider distribution above lower third of calf
Induration Presumes venous origin of secondary skin and subcutaneous changes (i.e., chronic edema with fibrosis, hypodermatitis)		Limited to perimalleolar area	Diffuse over lower third of calf	Wider distribution above lower third of calf

Medtronic Business Restricted

CONFIDENTIAL

056-F275, v B Clinical Investigation Plan Template

VENASEAL SPECTRUM Clinical Investigation Plan

MDT18034

Version 5.0

Page 135 of 164

Medtronic

Includes white atrophy and ipodermatosclerosis				
Active Ulcer Number	0	1	2	≥3
Active Ulcer Duration (longest active)	N/A	<3 mo	>3 mo but <1 y	Not healed for >1 y
Active Ulcer Size (largest active)	N/A	Diameter <2 cm	Diameter 2-6 cm	Diameter >6 cm
Use of Compression Therapy	0 Not used	1 Intermittent use of stockings	2 Wears stockings most days	3 Full compliance: stockings

Medtronic Business Restricted

CONFIDENTIAL

056-F275, v B Clinical Investigation Plan Template

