7.9.1.1.6 Sensitivity and Missing Data Analysis

It is recommended to perform an additional scoring of the TSQe that does not include Item 5, i.e. the Compression stockings question.

To account for missing data in the primary endpoint evaluation, two forms of imputation will be performed. For patients that have no baseline information collected, they will be assigned the average value of the TSQ in the control arm. For patients with a baseline visit and baseline information collected, multiple imputation will be performed as a sensitivity analysis. Subjects who do not obtain their VenousTSQe at 30 days, VenousTSQs at 30 days or the percentage of target vein treated at procedure will have these measurements imputed using PROC MI in SAS. The covariates to be used in the imputation model are age, gender, race, diabetes, CEAP classification, Historical Superficial and Deep Venous Treatment, Family History of Chronic Venous Disease, VCSS at baseline, 7 days and 30 days, Length of clinically relevant superficial truncal disease in target vein and treatment arms. Ten imputed data sets will be generated using regression method (REG option in PROC MI). The overall PROM scores for VenousTSQe and VenousTSQs and % target vein treated success and their standard errors will be generated for each of ten imputed data sets. PROC MIANALYZE in SAS will be used to summarize the overall treatment difference, standard error, and two-sided 95% confidence interval.

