3. Change in venous disease symptoms at 7 and 30 days, and at 6, 12, 24, 36, 48, and 60 months compared to baseline (7 and 30 days, 6 and 12 months only for VenaSeal vs. Surgical Stripping Study), as measured by the revised Venous Clinical Severity Score (rVCSS) and subject self-reporting.

Hypothesis

The following hypothesis will be tested:

$$H_0: \mu_A(t) - \mu_A(0) = \mu_C(t) - \mu_C(0)$$

$$H_a: \mu_A(t) - \mu_A(0) \neq \mu_C(t) - \mu_C(0)$$

where $\mu_A(t)$ and $\mu_C(t)$ are the mean VCSS scores at time point t in the VenaSeal™ system arm and the ETA or surgical stripping arm, respectively. Time t is any of 7 days, 30 days, 6, 12, 24, 36, 48, or 60 months.

Endpoint Definition

The VCSS is a validated 10-question venous disease severity measurement intended to evaluate the responses to changes in disease severity over time and in response to treatment. Each signs / symptom can have a grade ranging from 0 (absent) to 3 (severe). The total VCSS score is the sum of all questions. The score ranges from 0 (no venous disease) to 30 (severe venous disease).

Analysis Methods

The total VCSS value at baseline, at each visit, and change from baseline will be summarized for ITT population. The comparison will be done between the VenaSeal and control (ETA or Surgical Stripping) arms. In order to test the above stated statistical hypothesis, a Wilcoxon two-sample test with t approximation will evaluate the change in the score index from baseline to time t. The analysis will be performed using SAS code similar to:

```
proc npar1way data= vcsschg Wilcoxon plots = none;
  title "Wilcoxon test of Change in VCSS scores";
  class trtGroup;
```

```
var vcssdiff;  
where cpevent="XXX";  
run;
```

Additionally, a linear mixed effects model will be fit on VCSS scores with an interaction variable fit for time and study group. Time points include baseline and scheduled follow-up visits. The model will account for the correlation of scores within each subject. Likelihood ratio tests will be used to test for the significance of the study group effect and the time effect. Partial t-tests will be used to compare scores between study groups at specific time points.

The analysis will be performed using SAS code similar to:

```
PROC MIXED;  
  CLASS time trtGroup;  
  MODEL VCSS = time trtGroup time*trtGroup;  
  RANDOM INT / SUBJ=ptid corr=exch;  
RUN;
```

Determination of Subjects for Analysis

The analysis will consist of the ITT population.

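### The early rVCSS comparison counts compression use as disease severity, so if stocking use differs by arm at 7 and 30 days, part of any between-arm difference would reflect aftercare

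*Protocol*

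**What the plan says.** The protocol (Synopsis and 5.2.3, endpoint 14) defines the endpoint as "Change in venous disease symptoms at 7 and 30 days, and at 6, 12, 24, 36, 48, and 60 months compared to baseline", measured by the rVCSS and by subject self-report.

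The rVCSS form in protocol Appendix A (item 3) has ten items. The last is use of compression therapy: 0 for not used, 1 for "Intermittent use of stockings", 2 for stockings most days, and "3 Full compliance: stockings" at the top of the scale. It carries the same 0-3 weight as pain or edema.

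SAP 7.9.1.7 item 3 states that "The total VCSS score is the sum of all questions", gives a range of 0 to 30 with higher meaning worse, and tests the between-arm difference in change by a Wilcoxon test at every visit from day 7. It adds a mixed model on the same total. Under SAP 7.9.1.3 these p-values are not adjusted for multiplicity.

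On compression:
- Protocol 10.9 has subjects follow the site's usual post-operative instructions after discharge, and records each subject's "use of compression stockings upon discharge".
- Protocol 11.5, listing challenges of ETA that VenaSeal addresses, cites "rapid return to normal activities without the need for compression stockings following treatment".
- SAP 7.9.1.1.6 recommends an "additional scoring of the TSQe that does not include Item 5, i.e. the Compression stockings question", and SAP 7.9.1.1.4 leaves the stocking item out of the VenousTSQs score. No comparable step is planned for the rVCSS.

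**The concern.** Between baseline and the early visits, the compression item can move because of a discharge instruction rather than because the leg is better or worse. Two subjects with the same pain, edema and skin findings can differ by up to 3 points if one was told to wear stockings and complied. If wear differs by treatment, that difference enters the arm comparison under the label of venous disease symptoms.

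Protocol 11.5 suggests the likely direction: fewer wearers after VenaSeal, and so a lower (better) score in that arm. The trial is open label and nothing in the plan equalises compression between arms. A significant day 7 or day 30 result on the total could not then be attributed to signs and symptoms. The self-report part of endpoint 14 contains no compression item, but SAP 7.9.1.7 item 3 defines no analysis of it, so the full total is the only tested measure.

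**Working it through.** **The plan's own figure.** Ten items × 3 points = 30, the stated maximum. Without the compression item it would be 9 × 3 = 27. The item is therefore counted.

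**Inputs from the documents**
- rVCSS 6.5 (SD 2.4) at baseline and 1.8 (SD 1.4) at 1 month: the WAVES figures in protocol 4.1, the only rVCSS figures given.
- 264 subjects in the ETA study and 108 in the stripping study, randomised 1:1. With the 7% attrition stated for the 30-day VenousTSQ: 264 × 0.93 / 2 ≈ 123 and 108 × 0.93 / 2 ≈ 50 per arm.

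**Inputs assumed**
- Correlation between baseline and follow-up. SD of change = √(2.4² + 1.4² − 2·r·2.4·1.4), which is 2.1 at r = 0.5 and 2.8 at r = 0.
- Wear rates in each arm and the score that wearers receive.
- Two-sided α of 0.05 (none is stated for this endpoint).

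**Step 1: the difference that is just significant.** Formula: 1.96 × SD × √(2/n).
- ETA study, n = 123: 0.52 points (SD 2.1) to 0.70 (SD 2.8). At 3 points per wearer, dividing by 3 gives an excess of 17 to 23 percentage points of full-compliance wearers.
- Stripping study, n = 50: 0.82 to 1.10 points, or an excess of 27 to 37 percentage points.

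**Step 2: the difference that compression alone creates.** Spurious mean difference = item score × excess share of wearers. For a 20-point excess this is 3 × 0.20 = 0.6, 2 × 0.20 = 0.4 or 1 × 0.20 = 0.2 points.

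**Step 3: how often the planned test rejects.** Baseline and follow-up scores were simulated from the WAVES figures with r = 0.5, rounded and floored at 0, with no arm difference. A compression score was then added and change was compared by a two-sided Wilcoxon test. In each range, the upper end assumes no baseline wear and the lower end 30% baseline wear in both arms.

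| Wearers, VenaSeal vs control | Score per wearer | n per arm | Significant |
|---|---|---|---|
| 30% vs 30% | 3 | 123 | about 5% |
| 30% vs 50% | 3 | 123 | 34-46% |
| 30% vs 50% | 2 | 123 | 23-26% |
| 30% vs 50% | 1 | 123 | about 10% |
| 30% vs 50% | 3 | 50 | 15-22% |

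At score 3, essentially all rejections in the 30% vs 50% rows favour VenaSeal.

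**Cross-check.** A separate simulation with 20% baseline wear in both arms and 20% vs 40% wear afterwards gave 29-39% at score 3 for n = 123 (SD of change 2.8 and 2.1). With the compression item left out, rejection was about 3-7% in every scenario, which is the nominal 5% with simulation noise.

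**The case against.** **Arm-specific compression is not documented.** A reader might infer that ETA and stripping subjects wear stockings and VenaSeal subjects do not, so that the comparison is biased as it stands. The documents do not say this. Protocol 10.9 refers only to site-standard instructions. Protocol 11.5 says what VenaSeal does not need; it does not say what ETA subjects wear or for how long, and it is silent on stripping. Randomisation is stratified by site, so a site with one policy for both arms contributes no bias. This objection stands: a difference in wear is plausible, not established.

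**The larger rejection rates depend on favourable inputs.** At 30% vs 70% wear with every wearer scoring 3, the rate is 90-97%, but at score 1 without baseline wear it is about 29%. Small gaps or intermittent use would usually not reach significance. The WAVES figures are also totals that here stand in for the other nine items. All of this stands, and is why the size is given as a range.

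**The instrument is a validated total on a secondary endpoint.** The p-values are unadjusted and must be reported as such. Pain scores and the self-reported symptom list, both collected at days 7 and 30, contain no compression item and could expose a contradiction. Compression may itself ease pain or edema, so a 9-item score is not perfectly neutral either. These points argue against replacing the 0-30 total or making every claim conditional on the reduced score. They do not argue against showing the 9-item result beside it.

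**The AVVQ.** Question 5 asks "In the last two weeks, have you worn support stockings or tights", so the same mechanism could operate at day 30. The SAP's scoring attachment is not visible in the text, so the item's weight is unknown and no effect can be claimed.

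**Conclusion.** The scoring point is certain: the total tested at 7 and 30 days includes a 0-3 compression item, and no analysis without it is planned. The consequence is conditional. If stocking use differs by arm, part of any early rVCSS difference would reflect aftercare. A 20-point excess of control-arm wearers would then make the test significant in roughly 10% to 46% of trials in the ETA study, depending on how wearers score and on baseline wear, and in about 15-22% in the stripping study at score 3, against about 5% with equal wear.

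These figures rest on assumed wear rates, an assumed correlation and a borrowed attrition rate. The effect is absent where a site treats both arms alike, and may fade by day 30. The documents do not support concluding that the comparison is already biased towards VenaSeal, or that the published total should be abandoned. The point is an inexpensive safeguard on a secondary endpoint.

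**What to change.** In SAP 7.9.1.7 item 3:
- Pre-specify a supportive between-arm comparison of the 9-item rVCSS without the compression item (0-27) at 7 and 30 days, using the same Wilcoxon test, reported beside the 0-30 total.
- Tabulate the compression item by arm and visit, including baseline.
- State that an early between-arm rVCSS difference will be interpreted as a difference in symptoms only in light of the 9-item result.

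Optionally, in item 4, add a day 30 AVVQ score without question 5, using the rescaling for omitted questions that the SAP already contains.

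The cost is SAP wording and one derived score (two with the AVVQ option) from questionnaire items already on the forms. The downside is that the reduced score is not the published total, which is why both are shown. No change to compression practice is implied.

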4.1. Background

Venous Reflux Disease

Venous reflux disease (VRD) is a type of chronic venous disease (CVD) also known as venous insufficiency, a medical condition which affects the circulation of blood through the venous system of the lower extremities.

Medtronic Business Restricted

CONFIDENTIAL

056-F275, v B Clinical Investigation Plan Template

VRD of the lower extremities is a chronic and progressive disorder that is influenced by genetic and mechanical factors. It is believed to result from abnormal distensibility of the connective tissue present in the vein wall which ultimately results in venous dilatation and the failure of one-way valves present within the veins that direct the return of blood up the lower limb.¹ Incompetence of the valves and hypertrophy of the vein wall result in backflow, or venous reflux, and a pooling of the blood in the superficial veins. Reflux in the superficial venous system, commonly known as varicose veins, is estimated to affect 23% of all adults in the U.S.^{2,3} The Framingham study (1988) found that VRD was twice as prevalent as coronary heart disease and five times as prevalent as Peripheral Arterial Disease (PAD), and that up to 90% with symptomatic venous reflux are untreated.⁴ The more advanced stages of the disease affect approximately 5% of the population, with active ulcerative end stage disease present in about 1-2%.^{5,6} Great Saphenous Vein (GSV) insufficiency is the most common manifestation of varicose veins, although small saphenous (SSV), accessory saphenous, and duplicate veins that travel in parallel with the great and small saphenous veins (SSV) may also be affected.⁷

CVD is considered a major socioeconomic burden throughout the world with a budgetary impact greater than that of arterial disease.⁸ At least 63.9% of over 90,000 subjects in a Vein Consult Program, providing data from Europe, Latin America, the Middle East and the Far East, were diagnosed with CVD.⁹ It was recently described that in Western Europe, 2% of the annual healthcare budget is spent on chronic venous conditions (900 million Euros). Venous ulcers, which could be prevented by early therapy, contribute to 2 million lost workdays annually in the US.^{10,11}

Diagnosis and Classification of Disease Severity

Primary varicose veins initially develop in subcutaneous veins with diameters \leq 3 mm and are at first accompanied by few signs of CVD.¹² As the disease progresses, patients with varicose veins develop one or more symptoms that might include heaviness, aching or throbbing pain in the lower legs, cramps, restless leg syndrome, pruritus (itchiness), fatigue, swelling, and tenderness along the varicosity.¹³ Thrombophlebitis or bleeding from superficial varicose veins may be evident at diagnosis, as might the changes indicative of more advanced CVD such as edema, eczema, pigment changes, and ulcerations.^{6,14,15} The skin changes occur due to sustained venous hypertension concomitant with CVD.¹⁶

To adequately manage and treat venous reflux, the patient's CVD must be accurately diagnosed and classified, with a focus on the underlying venous problem. Patients typically undergo non-invasive Duplex Ultrasound (DUS) scanning in accordance with guidelines for investigation of lower limb disease. DUS is considered the gold standard in diagnosis of VRD and is used in pre- and postoperative assessment as well as during therapy for minimally invasive procedures. The GSV, Anterior Accessory Saphenous Vein (AASV), Posterior Accessory Saphenous Vein (PASV), thigh extension, and the SSV are the main superficial conduits imaged and tested for possible reflux prior to therapy.

Medtronic Business Restricted

CONFIDENTIAL

056-F275, v B Clinical Investigation Plan Template

One of the most well-accepted methods to evaluate the clinical signs of VRD is the Clinical, Etiological, Anatomical, and Pathophysiological (CEAP) classification system.^{2,6,17} The CEAP includes four categories of assessment: the clinical signs of the disease (C), the etiology or cause of the disease (E), the anatomy of the disease (A), and its underlying pathophysiology (P). Based upon these assessments, the severity of the disease can be classified. Stages range from CEAP 0 to CEAP 6. The clinical signs range from no visible signs of the disease to venous disease with multiple symptomology and active venous ulcerations.¹²

Treatment of VRD

Traditional surgical removal of the incompetent varicose veins was for many years considered a gold standard for the treatment of superficial venous reflux. Such an approach is generally achieved by surgical ligation and stripping of incompetent superficial truncal veins. This procedure may require use of general anesthesia and has been associated with significant perioperative morbidity including postoperative pain^{18,19} and slow recovery to normal daily activities.²⁰

Therapies are often combined for maximum treatment benefit. Sclerotherapy is a minimally invasive endovenous treatment option in which a sclerosing compound (foam or liquid) is delivered directly into the target vein. The injected compound produces endothelial damage and inflammation which lead to "sclerotic changes" in the vein wall and eventual fibrosis across the vein lumen.²¹ Sclerotherapy is often used adjunctively with other primary treatments and is allowable in this study as described in section 10, study procedures. Disadvantages of sclerotherapy as a primary treatment include poor efficacy requiring multiple treatments and prolonged compression hose therapy following treatment.²² General risks associated with sclerotherapy are similar to other endovenous therapies and include thrombophlebitis, localized phlebitis, hyperpigmentation, telangiectatic matting, and transient pain.^{21, 22, 23, 24}

In response to the complications associated with the surgical treatment, minimally invasive procedures have been developed. Interventions such as endothermal ablation (ETA) are minimally invasive procedures and include endovenous laser ablation (EVLA) that uses laser or radiofrequency ablation (RFA) that uses radiofrequency heating to seal the vessel. Heat is applied in both the therapies to ablate the target vein via a different medium. The underlying goal for all thermal ablation procedures is to deliver sufficient thermal energy to the wall of the incompetent vein segment to coapt the vein wall and achieve occlusion, and fibrosis. RFA involves delivery of controlled radiofrequency energy through a generator which heats a segment of the catheter which is inserted into the diseased vein. A tumescent anesthetic is administered around the vein, the catheter is inserted, and the radiofrequency energy is delivered to occlude the vein. The heat causes the vein to contract and occlude. EVLA involves use of a laser catheter and is inserted into the venous system via percutaneous access using duplex ultrasound (DUS) guidance or by open venotomy. A tumescent anesthetic is also administered around the vein, laser energy is applied to the inside of the vein and the vein is sealed. Despite EVLA and RFA being minimally invasive, there are

*Medtronic Business Restricted***CONFIDENTIAL**

056-F275, v B Clinical Investigation Plan Template

disadvantages and risks with ETA, including hematoma, thrombophlebitis, venous thrombosis, vessel perforation, skin burns, paresthesia of the leg, the need for multiple needle sticks to apply large volumes (150-1000 cc) of perivenous anesthetic (i.e., tumescent anesthesia), or injury to the sural or saphenous nerve.²⁵ Tumescent anesthesia is painful during administration and can lead to ecchymosis and longer recovery time.

The VenaSeal™ closure system was developed as a non-thermal, non-tumescent and non-sclerosant (NTNTNS) alternative to other available treatment options, specifically thermal and tumescent options which require the usage of tumescent anesthesia and involve risk of thermal injury.²⁵ The VenaSeal™ system uses a medical grade adhesive to eliminate the primary source of reflux by coaptating the vein walls. Closure of the insufficient vein is accomplished through polymerization of a cyanoacrylate-based adhesive delivered via a catheter, and the resultant acute coaptation of blood flow is followed by eventual encapsulation of the blockage.

Summary of VenaSeal™ Closure System Clinical Studies

Feasibility Study

The Feasibility Study was a prospective, single center study performed in the Dominican Republic to assess safety and VenaSeal™ effectiveness to treat VRD in the GSV. Effectiveness results of the Feasibility Study indicated a 94.7% closure rate at 6 months following the index procedure. Subjects were followed for 36 months in total. There were 4 Serious Adverse Events (SAEs) reported in 3 subjects, with 1 of the 4 determined to be related to the study device or study procedure. An additional 24 Adverse Events (AEs) were reported in 17 subjects. Finally, 1 Deep Vein Thrombosis (DVT) was observed at 31 months post-treatment in a hypercoagulable subject (unknown device relationship, not related to the procedure).

eSCOPE Post-Market Study

The eSCOPE Post-Market Study was a multicenter, prospective, single arm study conducted in Europe designed to record the clinical outcomes of the CE-marked VenaSeal™ closure system for its approved indications. The primary objective was to assess the role of the VenaSeal™ system in closure of incompetent GSVs in a routine clinical setting. Effectiveness and safety (AEs) were compared to appropriate literature reports as per individual study protocols to determine if the results of the treatment of reflux disease with the VenaSeal™ system were consistent with or better than the expectations of the medical community for alternative treatments, specifically endovenous laser thermal ablation and RFA. Effectiveness results indicated a 91.4% closure rate at 6 months, declining to 88.5% closure at 36 months. At 6 months, safety analysis observed 32 AEs, one of which was an unrelated serious adverse event.

VeClose IDE Pivotal Study

The VeClose Study was a randomized, prospective, multicenter study conducted to demonstrate safety and effectiveness of the VenaSeal™ system for the treatment of lower-extremity truncal reflux compared to RFA performed using the ClosureFast™ System. This study was conducted in the United States under Investigational Device Exemption (IDE) G120204, data from the study was used to support a premarket approval (PMA) application. The PMA Application was approved by the FDA on February 20, 2015.

The study's primary effectiveness endpoint was at 3 months. The primary safety assessment was performed at 1 month. The study was originally completed on April 10, 2017. The original results of the study, including 3-year follow-up data are summarized below.

A total of 242 subjects from 10 US clinical sites were treated in the study. There were 20 subjects treated and analyzed in the roll-in cohort and 222 subjects in the randomized cohorts (108 in VenaSeal™ system and 114 in RFA). The overall mean age was 50 years (range 25 – 70) and the study population was consistent with the known female predominance of venous disease, with primarily female subjects (80%). The majority of subjects (56.6%) entered the study with venous disease in the study limb classified as CEAP 2. Aching and pain were the 2 most frequently reported dominant symptoms, with over 25% of subjects reporting these symptoms. There were no statistically significant differences in the demographics or baseline parameters between the randomized groups (VenaSeal™ system and RFA).

Effectiveness was measured as vein closure at 3, 12, 24 and 36 months. At 3 months, the closure rate observed was 99.0% for the cyanoacrylate group and 96% for the RFA group decreasing to 94.4% by 36 months for the cyanoacrylate group and 91.9% for the RFA group.²⁶ There were no statistically significant differences in rates of any individual AEs between the randomized VenaSeal™ system group and the RFA group through 36 months. For both groups, the majority of subjects reported no AEs, and of those who reported AEs, the majority had only one event. A total of 156 AEs were reported in 100 subjects; 78 AEs in 47 VenaSeal™ system subjects, 15 AEs in 11 roll-in subjects, and 63 AEs in 42 RFA subjects. A total of 15 serious adverse events (SAEs) were reported in 12 subjects (5 VenaSeal™ system, 1 roll-in, and 6 RFA). All were assessed as unrelated to the study device or study procedure.^{26,27,28,29}

There was one report of death (due to liver cancer) in a VenaSeal™ system subject. The liver cancer death at Day 1098 post-procedure was assessed as unrelated to the study device or study procedure. There was one report of deep venous thrombosis (DVT) in the non-index limb in an RFA subject. There were no reports of Pulmonary Embolism (PE), no reports of allergic reactions to the VenaSeal™ adhesive (cyanoacrylate), and no reports of Unanticipated Adverse Device Effects (UADEs).

VeClose Five-Year Follow-up Extension Study

The VeClose Five-Year Follow-up Extension study was conducted to gain additional follow-up data from the patients enrolled in the VeClose IDE pivotal study described above. Patients treated in both the experimental and control study arms as well as in the roll-in cohort were assessed for a 60-month follow-up visit. The study was conducted under a separate protocol and no further intervention occurred under this protocol. A total of 89 subjects completed the 60-month visit, 9 subjects were from the roll-in cohort and 80 subjects from randomization cohort (47 subjects in VenaSeal™ system and 33 subjects in RFA). 53 subjects treated with the VenaSeal™ system (subjects enrolled in VenaSeal™ system + roll-in subjects) maintained a closure rate of 94.6% at 60 months. The closure rate for 33 subjects treated with RFA was 100%. Kaplan-Meier freedom-from-recanalization analysis demonstrated non-inferiority of the VenaSeal™ system compared to the RFA group at a significance level of 0.025 (non-inferiority based on one-sided 97.5% confidence interval with lower limit = -3.5%, and margin of -10%), through the 60-month follow-up period (91.4% vs. 85.2%, respectively). These rates remained unchanged from the 36-month follow-up visit, indicating that no new GSV failures occurred between the 36- and 60-month visits in either group. No SAE, PE, DVT or treatment limb AEs were reported in both the VenaSeal™ system cohort and the RFA cohort between 36-month and 60-month follow-up.³⁰

WAVES

In addition to the above industry-initiated studies, the Lake Washington Vascular VenaSeal™ Post-Market Evaluation (WAVES) study was a single-center multiple-investigator, single-arm prospective study investigating the use of the VenaSeal™ system in patients with symptomatic VRD. The study assessed the use of the VenaSeal™ system in GSVs (n=48), SSVs (n=8), and accessory saphenous veins (n=14).³¹ Diseased veins of up to 20 mm diameter were included. The WAVES protocol did not allow adjunctive tributary treatment at the time of the index procedure which were staged at 3 months post-index procedure.

There were 70 veins treated in 50 subjects. All primary target veins (48 GSV, 14 ASV, and 8 SSV) showed 100% closure using DUS at 7 days and 1 month. Complete closure at 3 months was achieved in 70 (99%) of the treated veins. By 3 months, the revised Venous Clinical Severity Score (rVCSS) (6.5 ± 2.4 at baseline to 1.8 ± 1.4 at 1 month and 3 month; p<0.001), Aberdeen Varicose Vein Questionnaire (AVVQ) (17.3 ± 7.9 at baseline to 8.9 ± 6.6 at 1 month and 6.5 ± 7.2 at 3 month; p<0.001), and the EQ VAS (84 ± 12 at baseline to 88.3 ± 8.7 at 1 month and 88.6 ± 10.6 at 3 month; p = 0.002) all showed statistical improvement between baseline and 1 month, and baseline and 3 month visits. The percentage of patients who required adjunctive treatments at three months was lower than had been predicted by the treating physicians (65% versus 96%, p=.0002).³² Procedural pain was mild with a Nominal Pain Rating (NPR) of 2.2 ± 1.8, and the mean time to return to work and normal activities was 0.2 ± 1.1 and 2.4 ± 4.1 days, respectively.

Phlebitis was the most common AE, occurring in the treatment area or side branches in 10 patients (20%), but resolving in all but one subject (2%) by one month. One patient developed body hives within the first week of the procedure which was resolved following antihistamine and steroid treatment, this was said to be consistent with a cyanoacrylate allergy. There were no DVTs or other SAEs. One patient had a thrombus extension at the seven-day DUS which was no longer evident at the one-month DUS. Between the 1-month and 3-month visits, there was one AE, knee bursitis in the treatment limb which was determined as unrelated to the procedure.³²

